4.1.4 Subject Enrollment and Randomization

Study participation begins (ie, a subject is “enrolled”) once written informed consent is obtained. Once informed consent is obtained, a MedImmune subject identification (SID) number will be assigned by the investigational site comprised of the 7-digit site number plus a progressive 4-digit number before screening evaluations may begin to assess study eligibility (inclusion/exclusion) criteria. The MedImmune SID number will be used to identify the subject during the screening process and throughout study participation, if applicable.

A master log of all consented subjects will be maintained at the site and will document all screening failures (ie, subjects who are consented but do not meet study eligibility criteria and/or are not randomized), including the reason(s) for screening failure. Subjects who meet study eligibility criteria and are randomized will be assigned a unique randomization code and a treatment arm.

If a subject who does not meet all the inclusion/exclusion criteria is randomized and treated in error, the investigator should inform the medical monitor immediately.

4.1.5 Withdrawal from the Study

Subjects are free to withdraw their consent to participate in the study (investigational product and protocol-defined assessments) at any time, without prejudice to further treatment. Subjects who withdraw consent will be asked about the reason(s) and the presence of any AEs. If the

subject is willing, the subject will be seen and assessed by the investigator (early discontinuation visit). AEs will be followed up, and all study medications should be returned by the subject. If a subject withdraws from further participation in the study, then no further study visits or data collection should take place.

4.1.6 Discontinuation of Investigational Product

An **individual subject** will not receive any further investigational product if any of the following occur in the subject in question:

- 1 Withdrawal of consent from further treatment with investigational product
- 2 Lost to follow-up
- 3 An AE that, in the opinion of the investigator or the sponsor, warrants discontinuation of further dosing
- 4 Pregnancy in a female subject (see Section 5.6.2 for additional details regarding pregnancy)
- 5 Signs or symptoms of severe hepatic impairment including abnormal laboratory values according to below:
 - (a) ALT and/or AST are $> 3 \times \text{ULN}$ and TBL $> 2 \times \text{ULN}$
 - (b) ALT and/or AST are $> 5 \times \text{ULN}$ for ≥ 14 consecutive days, at any time after initial confirmatory results
 - (c) ALT and/or AST are $> 8 \times \text{ULN}$
- 6 Average absolute (regardless of baseline value) cardiac QTc interval corrected for heart rate by QTcF > 500 msec, or an increase of QTcF > 60 msec above the baseline value, confirmed (persistent for ≥ 5 minutes) on a repeat 12-lead ECG
- 7 Any one of the following:
 - (a) **Tachycardia**, defined as resting supine pulse rate > 125 beats per minute persisting for at least 10 minutes
 - (b) **Symptomatic bradycardia**, defined as resting supine pulse rate < 40 beats per minute while awake, persisting for at least 10 minutes
 - (c) **Asymptomatic bradycardia**, defined as resting supine pulse rate < 30 beats per minute while awake persisting for at least 10 minutes
 - (d) **Hypertension**, defined as an increase from baseline in resting supine systolic > 40 mmHg or above 180 mmHg and persisting for at least 10 minutes and/or increase from baseline in resting supine diastolic BP > 20 mmHg or above 100 mmHg and persisting for at least 10 minutes
- 8 Persistent hyperglycemia detected as 2 or more laboratory plasma fasting glucose levels of > 260 mg/dL (14.4 mmol/L) taken at least 3 days apart are detected

Subjects who are permanently discontinued from receiving investigational product will be followed for protocol-specified assessments including the 28-day post-last-dose safety follow-up visit and continued follow-up of any AEs unless consent is withdrawn from further study participation, the subject is lost to follow-up, the subject starts alternative treatment, or the subject is enrolled in another clinical study.

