2 OBJECTIVES AND ENDPOINTS

2.1 Primary Objective(s) and Associated Endpoints

Table 1 Primary Objective(s) and Associated Endpoints

Type	Objective	Endpoint
Safety	Assess the safety and tolerability of MEDI0382 titrated up to the highest clinically tolerated dose (HCTD)	
 • Incidence of treatment-emergent adverse events and treatment-emergent serious adverse events through the end of the up-titration period (up to 8 weeks) and through the end of the follow-up period • Clinically important changes in 12-lead electrocardiogram, vital signs (including heart rate and blood pressure), physical examination, and clinical laboratory evaluations through the end of up-titration period (up to 8 weeks) and through the end of the follow-up period

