3.1.4 Management of Study Medication Related Toxicities

GI Tolerability

In this study, dose escalation may be limited by GI tolerability, specifically with respect to nausea and vomiting

Prior to receiving investigational product, subjects will be advised that transient nausea and vomiting are possible and will receive counseling about meal size and eating habits. Specifically, subjects will be advised to avoid administering the medication close to a large or high-fat meal; to consume small, frequent meals 4 to 5 times a day that are low in fat and insoluble fibers; and to stop eating when they are feeling full. Subjects will also be advised to avoid carbonated beverages, alcohol, and smoking to help prevent the occurrence of nausea and vomiting. This advice should be reiterated should symptoms of nausea and vomiting occur once investigational product dosing has initiated. If symptoms do not improve despite a change of dietary habits, metformin may be withheld for 3 days, or alternatively, subjects should be offered antiemetic therapy in accordance with institutional and local practice guidelines. A centrally acting antiemetic such as a 5HT-3 antagonist (eg, ondansetron) or cyclizine is the preferred treatment in the first instance, rather than a prokinetic agent such as domperidone or metoclopramide.

Hyperglycemia

In the unlikely event of suspected persistent hyperglycemia in a subject based on either symptoms of hyperglycemia (eg, thirst, polyuria, blurred vision), capillary blood glucose readings (eg, 3 readings > 260 mg/dL [14.4 mmol/L] within one week), the investigator should perform additional fasting blood glucose levels as necessary to further investigate, and subjects should be asked to monitor capillary plasma glucose levels up to 5 times per day. If 2 or more laboratory plasma fasting glucose levels of > 260 mg/dL [14.4 mmol/L] taken at least 3 days apart are detected, the subject should be discontinued from the study (Section 4.1.6), and rescue therapy should be considered in line with current local guidelines.

Hypoglycemia

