5.4.1 Time Period for Collection of Adverse Events

All AEs regardless of severity will be collected from randomization throughout the treatment period and including the follow-up period. All SAEs and any AEs related to study procedures will be recorded from the time of informed consent.

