5.4.2 Follow-up of Unresolved Adverse Events

Any AEs that are unresolved at the subject’s last AE assessment in the study are followed up by the investigator for as long as medically indicated, but without further recording in the eCRF. MedImmune retains the right to request additional information for any subject with ongoing AE(s)/SAE(s) at the end of the study, if judged necessary.

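### Section 4.1.6 ends safety data collection when a subject who stopped drug starts alternative treatment, although the primary safety endpoint runs to the end of follow-up

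*Protocol*

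**What the plan says.** Protocol Section 2.1 (Table 1) sets two windows for the primary safety endpoint. TEAEs and serious TEAEs are counted "through the end of the up-titration period (up to 8 weeks) and through the end of the follow-up period". Changes in ECG, vital signs, physical examination and laboratory tests are assessed "through the end of up-titration period (up to 8 weeks) and through the end of the follow-up period".

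Section 4.1.6 says that subjects who permanently stop investigational product continue with the protocol's assessments, "including the 28-day post-last-dose safety follow-up visit and continued follow-up of any AEs unless consent is withdrawn from further study participation". Loss to follow-up is a further exit. The list then adds two more: "the subject starts alternative treatment, or the subject is enrolled in another clinical study". The protocol does not define alternative treatment.

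Section 5.4.1 has no matching exception: "All AEs regardless of severity will be collected from randomization throughout the treatment period and including the follow-up period".

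On persistent hyperglycemia, Section 3.1.4 says that "the subject should be discontinued from the study (Section 4.1.6), and rescue therapy should be considered in line with current local guidelines". The section it cites governs stopping investigational product and keeps the subject in follow-up.

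Section 4.7.2 says that new glucose-lowering drugs should not be started during dosing or follow-up, except where the investigator sees a safety need and has discussed it with the medical monitor. It does not say that follow-up ends when one is started.

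In the SAP, the As-treated population holds every dosed subject (Table 3.2-1) and is used for all safety analyses (Section 3.5). Each subject counts once per preferred term or system organ class (Section 3.5.1). The only missing-data rule in the readable text, last observation carried forward, covers secondary efficacy (Section 3.4.2.2).

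**The concern.** Withdrawal of consent and loss to follow-up are unavoidable ends to data collection. Starting another drug is not: the subject still consents and can still be reached. Ending observation there leaves a gap in the window that the primary endpoint claims to cover.

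The gap can also depend on outcome. Apart from withdrawn consent, loss to follow-up and pregnancy, the reasons for stopping drug in Section 4.1.6 are AEs or hepatic, QTc, heart-rate, blood-pressure or glucose findings. For hyperglycemia, the protocol itself links the stop to a possible new treatment. A safety finding may therefore lead to the loss of later safety data on the same subject.

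The last column of Table 7, which serves as both the 28-day visit and the early discontinuation visit, shows what is exposed: targeted physical examination, vital signs, ECG, hematology, chemistry, lipids, calcitonin, urinalysis and ADA. Within Table 7, calcitonin appears only there. Under Section 4.3.5, a positive end-of-study ADA result triggers the three-month sample, so a missed visit can also break that sequence.

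**Working it through.** **1. The passages side by side**

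- Endpoint window (Section 2.1): to the end of follow-up, no exception.
- AE collection (Section 5.4.1): to the end of follow-up, no exception.
- New glucose-lowering drug (Section 4.7.2): possible for safety; no statement that follow-up ends.
- After stopping drug (Section 4.1.6): assessments, 28-day visit and AE follow-up end if alternative treatment starts.
- Hyperglycemia (Section 3.1.4): refers to the study, but cites a section that stops the drug only.

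The last two entries do not agree with the first three or with each other.

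**2. Arm sizes**

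Section 4.8.2 gives 8 + 12 = 20 subjects, randomized 3:1 in each cohort. That is 6:2 and 9:3, or 15 on MEDI0382 and 5 on placebo. The size is described as empirical, and the readable text gives no power calculation to reproduce. Section 4.1.7 rules out replacement.

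**3. Length of the exposed window**

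Up to 56 days of titration + 21 of extension + 28 of follow-up = 105 days. Follow-up is 28/105 = 26.7% of that. The exit covers all assessments specified in the protocol, so a subject who stops early may also lose the rest of the up-titration window.

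**4. What happens to incidence**

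- If the subject stopped for a TEAE, that subject is already counted, so overall any-TEAE incidence changes by 0.
- For an event not yet counted (a new preferred term, an SAE, a late ECG or laboratory change), the subject stays in the denominator as a non-event. Each missed event lowers observed incidence by 1/15 = 6.7 points on MEDI0382 or 1/5 = 20 points on placebo.

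**5. Expected understatement on MEDI0382**

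The documents give no rates for stopping drug or for starting alternative treatment, so the inputs here are assumptions. Let k of 15 subjects be truncated, q be their risk of a new event after the cut-off, and p the risk in the others.

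- True incidence: [(15 − k)p + kq]/15
- Observed incidence: (15 − k)p/15
- Difference: kq/15, whatever p is

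| k truncated | q = 10% | q = 30% | q = 50% |
|---|---|---|---|
| 1 | 0.7 points | 2.0 | 3.3 |
| 2 | 1.3 | 4.0 | 6.7 |
| 3 | 2.0 | 6.0 | 10.0 |

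For example, 1 × 0.10/15 = 0.7 points and 3 × 0.50/15 = 10.0 points.

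**The case against.** A reader might infer that the primary endpoint loses the subjects most likely to have events. The documents do not support that. Every dosed subject stays in the As-treated set, all TEAEs before the cut-off count, and AEs leading to discontinuation are summarized separately (SAP Section 3.5.3). Only what happens after the cut-off is exposed.

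A reader might also infer that most subjects who stop will soon receive another glucose-lowering drug. Section 4.7.2 restricts such drugs to safety need, metformin continues throughout, and Section 3.1.4 itself regards persistent hyperglycemia as unlikely. For stops due to nausea, QTcF, heart rate, blood pressure or liver tests, nothing links the stop to a new diabetes drug within 28 days. This argument stands and makes the number affected probably small. It does not remove the exit.

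Other provisions soften the loss. The 28-day column of Table 7 doubles as the early discontinuation visit, and Section 3.1.1.1 allows the final visit at a convenient time after discontinuation. Some assessments may be recovered this way, but Section 4.1.5 describes that visit only for withdrawn consent, and Section 4.1.6 does not require it here. Section 5.4.2 has unresolved AEs "followed up by the investigator for as long as medically indicated, but without further recording in the eCRF", which protects the subject but adds nothing to the analysis.

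It is tempting to apply the Section 4.1.5 instruction that "then no further study visits or data collection should take place" to these subjects. That section governs withdrawal from the study, not stopping drug and starting another treatment. The loose wording in Section 3.1.4 could invite that reading, which is a reason to reconcile it.

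Finally, one could compare zero-event upper limits for 15 and 12 subjects. That treats truncated subjects as contributing nothing, and a count of three has no source in the documents.

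**Conclusion.** The point holds as a gap in safety data collection. Section 4.1.6 permits observation to end for a reason that can follow from a safety outcome. This conflicts with the primary endpoint window and with Section 5.4.1, and the readable SAP has no rule for the truncated data. Section 3.1.4 separately contradicts the section it cites.

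Overall any-TEAE incidence is little affected. The exposure is in later new events and SAEs, and in the 28-day ECG, vital-sign, laboratory and ADA results. For incidence the direction is downward, because missed events leave the denominator unchanged. The size is 6.7 points per missed new event on MEDI0382 and 20 on placebo. The range of 0.7 to 10 points on MEDI0382 rests wholly on the assumed 1 to 3 truncated subjects and 10% to 50% late-event risk. The documents give no basis for saying which arm would be affected more.

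Confidence is medium: the text is clear, but its effect in practice is unknown.

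**What to change.** - In Section 4.1.6, remove the start of alternative treatment as a reason to end data collection for subjects who still consent. Continue AE recording and the 28-day assessments already in Table 7.
- Record the start date of the new treatment. Flag data after that date and show them in a sensitivity table.
- Reconcile Sections 3.1.4, 4.1.6, 4.7.2 and 5.4.1 on whether study follow-up continues. Define alternative treatment wherever the term is kept. This concerns data collection only; no treatment, rescue or stopping rule need change.
- In the SAP, state how truncated safety follow-up is reported, for instance by giving the number of such subjects per arm.

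The cost is a short amendment and at most one already-scheduled visit for a few subjects. The drawback is that some events after the switch may reflect the new treatment; the flag lets a reader separate them. This is a cheap improvement.

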4.1.7 Replacement of Subjects

Subjects will not be replaced.

For Cohort 1, up to 3 additional subjects may be screened and enter the run-in period to ensure that a sufficient number of subjects are randomized. If these subjects are not required for Cohort 1, they are available to be randomized into Cohort 2.

If the screening visit for these subjects is outside the allowed time window, they will undergo a second screening and run in period in order to be eligible for Cohort 2. When these subjects are randomized, the data from the second screening/run in (if needed) will be used for reporting.

4.1.8 Withdrawal of Informed Consent for Data and Biological Samples

If a subject withdraws consent to the use of mandatory biological samples, the samples will be disposed of/destroyed, and the action documented. If samples are already analyzed, MedImmune is not obliged to destroy the results of this research. As collection of the biological samples is an integral part of the study, then the subject is withdrawn from further study participation.

The principal investigator:

- Ensures subjects' withdrawal of informed consent to the use of donated samples is notified immediately to MedImmune.
- Ensures that biological samples from that subject, if stored at the study site, are immediately identified, disposed of/destroyed, and the action documented.
- Ensures the organization(s) holding the samples is/are informed about the withdrawn consent immediately and that samples are disposed of/destroyed, the action documented and the signed document returned to the study site.
- Ensures that the subject and MedImmune are informed about the sample disposal.

MedImmune ensures the organizations holding the samples is/are informed about the withdrawn consent immediately and that samples are disposed of/destroyed and the action documented and returned to the study site.

4.2 Schedule of Study Procedures

Whenever vital signs, 12-lead ECGs, and blood draws are scheduled for the same nominal time, the blood draws should occur last. The timing of the first 2 assessments should be such that it allows the blood draw (eg, PK blood sample) to occur at the proper nominal time.

4.2.1 Enrollment/Screening Period

[Table 5](#) shows all procedures to be conducted at the screening visit. Assessments should, where practically possible, be performed in the order shown in the table.

Table 5 Schedule of Screening and Run-in Procedures

Study Period	Screening ^a	Run-in
Visit Number	V1	V2
Procedure / Study Day	Day -25 to -12	Day -11 to -3 ¹
Written informed consent/assignment of SID number [#]	X	
Optional informed consent for sample for future genetic research	X	
Optional informed consent for sample for future non-genetic research	X	
Medical history, including smoking and alcohol history	X	
Physical examination (full) ^b	X	
Verify eligibility criteria	X	
Weight ^c , height, and BMI calculation	X	
Demographics	X	
12-lead ECG ^d	X	
Vital signs (BP, pulse, body temperature, RR) ^e	X	
Collect blood for:		
Serum chemistry	X	
Coagulation panel	X	
Hematology	X	
HbA1c ^f	X	
Plasma glucose ^g	X	
Calcitonin	X	
HIV-1 and -2 antibodies; hepatitis B and C serology	X	
Triglycerides	X	
Pancreatic amylase, lipase	X	
Serum b-HCG (pregnancy test, females only)	X	
FSH (postmenopausal females only) ^m	X	
Collect urine for:		
Urinalysis	X	
Urine drug and alcohol screen ^h	X	

Table 5 Schedule of Screening and Run-in Procedures

Study Period	Screening ^a	Run-in
Visit Number	V1	V2
Procedure / Study Day	Day -25 to -12	Day -11 to -3 ^l
SC injection training/demonstration ^j	X	X
[REDACTED] ⁱ		[REDACTED]
ABPM ^k		X
Glucometer and diary dispensed		X

[figure not shown]
ABPM = ambulatory blood pressure monitoring; BMI = body mass index; BP = blood pressure; [REDACTED]
[REDACTED] ECG = electrocardiogram; FSH = follicle-stimulating hormone; HbA1c = hemoglobin A1c; HIV = human immunodeficiency virus; SC = subcutaneous; SID = subject identification; V = visit

[figure not shown]
- ^a Screening period may be extended to Day -42 in Cohort 2 if washout of oral anti-diabetic therapy (other than metformin) is required
 - ^b Only the screening physical examination will be a full examination. For all time points thereafter, only a targeted physical examination is required.
 - ^c Body weight should be measured in the morning while the subject is fasted and prior to breakfast, after the subject has toileted and removed bulky clothing, including shoes. Calibrated scales should be used.
 - ^d A single digital ECG recording should be performed after the subject has rested for 10 minutes.
 - ^e BP and heart rate should be measured once at heart level in the non-dominant arm where possible, with the subject supine for 10 minutes prior to the measurement (rest period for ECG will suffice).
 - ^f HbA1C to be re-checked prior to the start of the run-in period only for those subjects washing out from a second anti-hyperglycemic agent
 - ^g **Fasting** plasma glucose to be checked prior to the start of the run-in period for those subjects washing out from a second anti-hyperglycemic agent
 - ^h An alcohol breath test is an acceptable alternative to an alcohol urine test.
 - ⁱ Subjects should be shown the device and given an explanation as to how it is worn.
 - ^j Subject's ability to administer a SC injection will be verified by undergoing a single SC injection using normal saline provided by the site. Willingness to perform this for the duration of the study should be discussed with the subject. Further training may be given during the run-in period as required.
 - ^k Subjects will be fitted with the ABPM device while at the clinical unit, which may involve practice inflations. The subject will then wear the monitor/cuff for approximately 24 hours (including overnight at home) and will remove the device at home at the end of the 24-hour period.
 - ^l [REDACTED]
 - ^m FSH should only be checked in female subjects who are post-menopausal and have no previous confirmatory laboratory FSH result available.
- # Collection of Informed consent may occur prior to the other screening assessments, on a separate visit if required

[figure not shown]
[REDACTED]

[figure not shown]
[REDACTED]

[REDACTED]

4.2.3 Treatment Extension at HCTD and Follow-up Period

Table 7 shows all procedures to be conducted during the treatment extension and follow-up period.

Table 7 Schedule of Procedures for Treatment Extension at HCTD and Follow-up Periods

Study Period Timepoint	Treatment Extension at HCTD				Follow-up			
	Day 1 of TE	Day 7 of TE	Day 20 of TE	Day 21 of TE	Day 1 post last dose	Day 2 post last dose	Day 3 post last dose	28 days post last dose/EDV (\pm 3 days)
Procedure/Visit Number	V11	V12	V13		V14	V15	V16	
Outpatient clinic visit		X			X ^a	X ^a	X ^a	X
Inpatient clinic visit	X		X	X				
Day of discharge from clinical unit on completion of assessments	X				X			
Fasting for minimum of 10 hours prior to the morning of the study day				X				
Standardized meal day ^b				X				
Targeted physical examination			X					X
Vital signs (BP, pulse, body temperature) ^c		X	X	X				X
ABPM ^d				X				
ECG ^e	X	X		X	X	X	X	X
Body weight ^f		X		X				X
Investigational product administration	Subject will self-administer investigational product daily via SC injection							
Blood tests								

Table 7 Schedule of Procedures for Treatment Extension at HCTD and Follow-up Periods

Study Period Timepoint	Treatment Extension at HCTD				Follow-up			
	Day 1 of TE	Day 7 of TE	Day 20 of TE	Day 21 of TE	Day 1 post last dose	Day 2 post last dose	Day 3 post last dose	28 days post last dose/EDV (± 3 days)
Procedure/Visit Number	V11	V12	V13		V14	V15	V16	
Hematology panel				X				X
Serum Chemistry panel				X				X
Fasting plasma glucose				X				
Fasting lipase and amylase				X				
Calcitonin								X
Fasting lipid panel				X				X
HbA1c				X				X
PK for MEDI0382 ^g	X	X		X	X	X	X	
PK for metformin ^h	X	X		X	X	X	X	
ADA				X				X
Blood sample for optional future non-genetic research				X				
Urine collection for:								
Urinalysis (dipstick; predose as applicable)		X	X					X
Pregnancy test (if applicable)			X					X

Table 7 Schedule of Procedures for Treatment Extension at HCTD and Follow-up Periods

Study Period	Treatment Extension at HCTD				Follow-up			
Timepoint	Day 1 of TE	Day 7 of TE	Day 20 of TE	Day 21 of TE	Day 1 post last dose	Day 2 post last dose	Day 3 post last dose	28 days post last dose/EDV (± 3 days)
Procedure/Visit Number	V11	V12	V13		V14	V15	V16	
								
AEs/SAEs	Throughout study							
Concomitant medications	Throughout study							

ADA = anti-drug antibody; AE = adverse event; ABPM = ambulatory blood pressure monitoring; BP = blood pressure;  ECG = electrocardiogram; EDV = early discontinuation visit; HbA1c = hemoglobin A1c; PK = pharmacokinetics; SAE = serious adverse event; SC = subcutaneous; TE = treatment extension

- a Subjects may choose to remain in the clinical unit as an inpatient if it is more convenient.
- b Subjects will eat a standardized breakfast, lunch and evening meal at approximately 9 am, 1 pm and, 6 pm. No further food should be consumed until any fasted assessments have been carried out the following morning. Water is permitted ad libitum.
- c Vital Signs Schedule (BP, pulse, and temperature): on days where ABPM is due to be checked a predose set of vital signs should be performed prior to application of the ABPM cuff. Blood pressure should be measured once at heart level in the nondominant arm where possible,  with the subject supine for 10 minutes prior to the measurement. For time points where ECG recording precedes vital sign measurement, the 10-minute rest in the supine position prior to the ECG suffices for the rest prior to vital sign measurement. Vital signs should be measured predose (where applicable) on a given day.
- d ABPM device will be worn for 24 hours while in the clinical unit
- e A triplicate ECG recording will be collected on Days 1 and 7 of TE, predose; Day 21 of TE; predose, 1, 2 (± 15 minutes); 4, 6, 8, and 12 and 24, 48, and 72 (± 30 minutes) hours postdose. The ECG triplicate recording should be done prior to the PK samples being taken.
- f Body weight should be measured in the morning while the subject is fasted and prior to breakfast, after the subject has toileted and removed bulky clothing including shoes. Calibrated scales should be used.
- g PK Sampling Schedule for MEDI0382: Days 1 and 7 of TE, predose; Day 21 of TE; predose, 1, 2 (± 15 minutes); 4, 6, 8, and 12 and 24, 48, and 72 (± 30 minutes) hours postdose.
- h PK Sampling Schedule for Metformin: Days 1 and 7 of TE, predose; Day 21 of TE; predose, 1, 2 (± 15 minutes); 4, 6, 8, and 12 hours post dose. Further predose samples should be taken on Days 1, 2 and 3 post last MEDI0382 dose. On days where metformin PK samples are collected, the dose, time and date of the last metformin dose should be recorded relative to the samples taken
- i 

